7.1.4 Discontinuation of study treatment

Patients may voluntarily discontinue from the study treatment for any reason at any time. If a patient decides to discontinue from the study treatment, the investigator should make a reasonable effort (e.g., telephone, e-mail, letter) to understand the primary reason for this decision and record this information in the patient's chart and on the appropriate CRF pages. They may be considered withdrawn if they state an intention to withdraw, fail to return for visits, or become lost to follow-up for any other reason.

The investigator may discontinue study treatment for a given patient if he/she believes that continuation would be detrimental to the patient's well-being.

Study treatment must be discontinued under the following circumstances:

- Emergence of specific adverse events or laboratory abnormalities under some circumstances outlined in [Section 6.3](#).
- Failure to achieve CR or CRi with adequate blood count recovery in induction or relapse from CR or CRi with adequate blood count recovery.
- Pregnancy (pregnancy will be followed for outcome)
- Any other protocol deviation that results in a significant risk to the patient's safety

The appropriate personnel from the site and Novartis will assess whether study treatment should be discontinued for any patient whose treatment code has been broken inadvertently for any reason.

Patients who discontinue study treatments should NOT be considered withdrawn from the study. They should return for the assessments indicated in [Section 7.2.1](#). If they fail to return for these assessments for unknown reasons, every effort (e.g., telephone, email, and letter) should be made to contact them as specified in [Section 7.1.9](#).

For patients who discontinue treatment for reasons other than documented failure to achieve CR or CRi with adequate blood count recovery in induction phase or relapse from CR or CRi with adequate blood recovery, death, loss to follow-up, or withdrawal of consent, will continue to be followed for efficacy assessment and survival.

The investigator (or designee) must also contact the IRT to register the patient's discontinuation from study treatment.

7.1.4.1 Replacement policy

Not applicable

7.1.5 Withdrawal of consent

Subjects may voluntarily withdraw consent to participate in the study for any reason at any time. Withdrawal of consent occurs only when a subject:

- Does not want to participate in the study anymore, and
- Does not allow further collection of personal data

In this situation, the investigator should make a reasonable effort (e.g. telephone, e-mail, letter) to understand the primary reason for the subject's decision to withdraw his/her consent and record this information.

Study treatment must be discontinued and no further assessments conducted, and the data that would have been collected at subsequent visits will be considered missing.

Further attempts to contact the subject are not allowed unless safety findings require communicating or follow-up.

All efforts should be made to complete the assessments prior to study withdrawal. A final evaluation at the time of the subject's study withdrawal should be made as detailed in the assessment table.

Novartis will continue to keep and use collected study information (including any data resulting from the analysis of a subject's samples until their time of withdrawal) according to applicable law.

For US and Japan: All biological samples not yet analyzed at the time of withdrawal may still be used for further testing/analysis in accordance with the terms of this protocol and of the informed consent form.

For EU and RoW: All biological samples not yet analyzed at the time of withdrawal will no longer be used, unless permitted by applicable law. They will be stored according to applicable legal requirements.

7.1.6 Follow up for safety evaluations

[figure not shown]
All patients must have safety evaluations for 30 days, after the last dose of study treatment (including cytarabine, daunorubicin/idarubicin or midostaurin/placebo).

Data collected should be added to the Adverse Events CRF and the Concomitant Medications CRF.

7.1.7 Follow up for efficacy evaluations

Patients who discontinue study treatment for reasons other than death, failure to achieve CR or CRi with adequate blood count recovery in the induction phase or relapse from CR or CRi with adequate blood count recovery will continue to have post-treatment assessments as outlined in [Section 7.1](#) until relapse or death.

During this phase, the following data will be collected:

- Antineoplastic therapy/transplantation after discontinuation of treatment: every 3 months including start of new line, best response, and relapse date etc...

The following assessments will be performed:

- Physical examination for extramedullary disease assessment, blood samples for hematology [REDACTED]: every 3 months
- Bone marrow aspirate/biopsy for disease assessment [REDACTED]: after first 3 months after completion of post-consolidation therapy and at relapse.
- Questionnaires (EQ5D-5L, FACT with FACT-Leu) [REDACTED] every 6 months during the first two years and then yearly.

Patients will be followed in post-treatment follow up until relapse or end of study, whichever occurs first.

7.1.8 Survival follow up

Patients will enter the survival follow-up phase once they complete the safety follow up period (30 days after the last dose of midostaurin/placebo) in case of induction failure or have relapse during post-treatment follow-up. Patients will then be contacted by telephone every 3 months +/- 2 weeks or have a visit to follow up on their survival status. Any new antineoplastic medications that have been started since the last contact date will also be collected during these phone calls or visits.

7.1.9 Lost to follow-up

For patients whose status is unclear because they fail to appear for study visits without stating an intention to withdraw consent, the investigator should show "due diligence" by contacting the patient, family or family physician as agreed in the informed consent and by documenting in the source documents steps taken to contact the patient, e.g. dates of telephone calls, registered letters, etc. A patient should not be considered lost to follow-up until due diligence has been completed. Patients lost to follow up should be recorded as such on the appropriate Disposition CRF.

[figure not shown]
7.2 Assessment types

7.2.1 Efficacy assessments

Efficacy assessments will be performed according to the IWG criteria for AML ([Cheson et al 2003](#), [ELN 2017 / Döhner et al 2017](#)). The investigator assessment will be used for the efficacy analyses. Response criteria in AML are described in [Table 7-2](#):

Table 7-2 Response classification in AML at a given evaluation time (Cheson 2003, ELN 2017 / Döhner et al 2017)

Response category	Definition [#]
Complete remission (CR)	Bone marrow < 5% blasts no blasts with Auer rods

Response category	Definition [#]
	
Peripheral blood neutrophils $\geq 1.0 \times 10^9/L$ platelets $\geq 100 \times 10^9/L$ no blasts
 
No evidence of extramedullary disease (such as CNS or soft tissue involvement). Transfusion independent (see Section 7.2.1.6).

Complete remission with incomplete hematologic recovery (CRi)
	
Bone marrow < 5% blasts no blasts with Auer rods
 
Peripheral blood[#] neutrophils < $1.0 \times 10^9/L$ and/or platelets < $100 \times 10^9/L$ no blasts
 
No evidence of extramedullary disease (such as CNS or soft tissue involvement).
 
CRi with adequate blood count recovery is defined as the following: Bone marrow < 5% blasts no blasts with Auer rods
 
Peripheral blood[#] Neutrophils $\geq 1.0 \times 10^9/L$ and $50 \times 10^9/L \leq$platelets < $100 \times 10^9/L$ no blasts
 
No evidence of extramedullary disease (such as CNS or soft tissue involvement).

Partial remission (PR)
	
Bone marrow < 5% blasts AND presence of blasts with Auer rods OR $\geq 50\%$ decrease from baseline in blasts in bone marrow AND blast count in bone marrow is 5% to 25%
 
Peripheral blood neutrophils $\geq 1.0 \times 10^9/L$ platelets $\geq 100 \times 10^9/L$ no blasts
 
No transfusion of neutrophils/platelets within 2 days preceding the assessment (see Section 7.2.1.6).

No Response
	
Failure to attain the criteria needed for any response categories or relapse

Response category	Definition#
Relapse from CR or CRi	Only in patients with a CR or CRi with adequate blood count recovery. Any of the following: Reappearance of blasts in peripheral blood OR ≥ 5% blasts in bone marrow OR (Re-)appearance of extramedullary disease
Unknown	In case the response assessment was not done or the assessment was incomplete.

If not defined otherwise, all of the criteria apply.

[figure not shown]
Response assessment will be performed by investigator between Day 21-28 of each cycle of the induction, the consolidation and the post-consolidation phases. Response assessment will be re-performed for patients achieving CRi without adequate blood count recovery up to 3 weeks after day 28 of each cycle. Moreover, patient can be assessed any time if clinically indicated.

Treatment failure includes patients who failed to achieve a CR or CRi with adequate blood count recovery up to the end of induction cycle 2. The following categories will only be assessed in case of induction treatment:

Category	Definition
Primary refractory disease	No CR nor CRi with adequate blood count recovery after 2 cycles of induction treatment; excluding patients with death in aplasia or death due to indeterminate cause
Death in aplasia	Deaths occurring ≥7 days following completion of induction therapy while cytopenic; with an aplastic or hypoplastic bone marrow obtained within 7 days of death, without evidence of persistent leukemia (< 5% blasts in bone marrow, no Auer rods in blasts and/or no extramedullary disease)
Death from indeterminate cause	Deaths occurring before completion of therapy, or <7 d following its completion; or deaths occurring ≥7 d following completion of induction therapy with no blasts in the blood, but no bone marrow examination available

Induction therapy

Between Day 21-28 of the first induction cycle, a bone marrow aspirate/biopsy will be performed to determine the presence of residual leukemia (≥ 5% blasts) according to the International Working Group (IWG) criteria for AML ([Cheson et al 2003](#), [ELN 2017](#) / [Döhner et al 2017](#)). If the Day 21-28 bone marrow aspirate/biopsy shows <5% blasts and the response assessment is CR or CRi without adequate blood count recovery, then it is not necessary to repeat bone marrow aspiration/biopsy while patient is under platelet and/or neutrophil recovery but a new blood count assessment will be performed to determine if the patient has achieved CR or CRi with adequate blood count recovery to be able to move to consolidation phase. If the response is CRi without adequate blood count recovery between Day 21-28, the cycle will be prolonged up to two weeks for blood count recovery (i.e. day 42). If the patient has reached CR or CRi with adequate blood count recovery, the patient will be

able to move to consolidation phase. Otherwise, the patient will receive a second cycle of induction therapy.

If a patient receives a second course of induction therapy, a bone marrow aspiration/biopsy between Day 21-28 of the second induction cycle will be performed to determine if the patient has achieved CR or CRi with adequate blood count recovery. If the response is CRi without adequate blood count recovery between Day 21-28, the cycle will be prolonged up to three weeks for blood count recovery. If no adequate blood count recovery is reached, the patient will be considered as treatment failure and will be discontinued from study treatment and followed for survival and post treatment therapies. Otherwise, the patient will move to consolidation phase. Of note, the bone marrow results obtained between Day 21-28 can be used retrospectively to determine response level by Day 49 (Day 28 plus 3 weeks).

Therefore, the maximum duration of the induction phase cannot exceed 93 days: 28 days (planned duration of cycle 1) + 14 days (i.e. 2 weeks for blood count recovery period)) + plus 1 day prior to the start of the next cycle + 28 days (planned duration of cycle 2) + 21 days (i.e. 2 weeks blood count recovery period)) + plus 1 day prior to the start of the next cycle.

7.2.1.1 Consolidation therapy:

A bone marrow and blood count examination will be performed to evaluate for continued remission (CR or CRi with adequate blood count recovery) between Day 21-28 of each cycle of consolidation. For each cycle, if the patient achieves CR or CRi with adequate blood count recovery up to 3 weeks after day 28 of each cycle, the patient will receive the next treatment cycle. Of note, the bone marrow results obtained between Day 21-28 can be used retrospectively to determine response level by day 49 (Day 28 plus 3 weeks).

7.2.1.2 Post-Consolidation therapy:

A bone marrow examination will be performed to evaluate for continued remission (CR or CRi with adequate blood count recovery) prior the start of the post-consolidation therapy, at the start of Cycle 4, Cycle 7 and Cycle 10, and at the end of Cycle 12 of post-consolidation therapy or at any time at suspected relapse.

7.2.1.3 Post-treatment follow-up:

A bone marrow examination will be performed to evaluate for continued remission (CR or CRi with adequate blood count recovery) 3 months after completion of post-consolidation therapy. A bone marrow examination will also be performed at any time of relapse.

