6.4.1 Permitted concomitant therapy

Supportive therapy including prophylactic antibiotic and antifungal treatments, transfusions, growth factors etc. will be administered at the discretion of the investigators according to standard of care.

The patient must be told to notify the investigational site about any new medications he/she takes after the start of the study drug. All medications (other than study drug) and significant non-drug therapies (including physical therapy, herbal/natural medications and blood transfusions) administered during the study must be listed on the Prior or Concomitant non-drug therapies/procedures CRF.

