7.2.1.6 Evaluation of transfusion dependency

Information on transfusion dependency will be assessed at baseline as well as during the course of the trial for all patients. Transfusion of blood products will be recorded in a separate module of the CRF. The type of transfusion, start and end date as well as the volume of blood product will be captured at each visit with hematologic assessment.

A period of at least 2 days without any transfusion has been taken as a convention to define the status of transfusion independence to assess a CR or CRi with adequate blood count recovery. A patient who has received a blood transfusion within 2 days preceding a response assessment (i.e. CR) will be considered transfusion dependent at the time of this response assessment.

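### Table 7-2 gives no remission category to a patient with clear marrow, full counts and a recent transfusion, and it conflicts with Section 7.2.1.6 on CRi, so induction response (and hence EFS) can be misclassified or classified inconsistently

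*Protocol*

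**What the plan says.** Protocol Table 7-2 (Section 7.2.1) sets the response categories. Its footnote makes every criterion in a row apply unless stated otherwise. Counts below are × 10⁹/L.

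- **CR:** marrow blasts below 5% without Auer rods, neutrophils at least 1.0, platelets at least 100, no blood blasts, no extramedullary disease, and "Transfusion independent (see Section 7.2.1.6".
- **CRi:** the same marrow, with "neutrophils < $1.0 \times 10^9/L$ and/or platelets < $100 \times 10^9/L$ no blasts". No transfusion condition is listed.
- **CRi with adequate blood count recovery:** the same marrow, with "Neutrophils $\geq 1.0 \times 10^9/L$ and $50 \times 10^9/L \leq$platelets < $100 \times 10^9/L$ no blasts". No transfusion condition is listed.
- **PR:** Auer rods, or 5–25% marrow blasts after a fall of at least half, and "No transfusion of neutrophils/platelets within 2 days preceding the assessment (see Section 7.2.1.6".
- **The residual category, called No Response, is worded as:** "Failure to attain the criteria needed for any response categories or relapse".

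Protocol 7.2.1.6 takes at least 2 days free of any transfusion as the convention "to define the status of transfusion independence to assess a CR or CRi with adequate blood count recovery". Its next sentence, on patients transfused inside that window, names only CR in brackets.

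Protocol 4.2 and the protocol summary describe adequate recovery as neutrophils at least 1.0 and platelets at least 50, with no upper platelet limit and no transfusion condition. Protocol 6.4.1 permits transfusion: "Supportive therapy including prophylactic antibiotic and antifungal treatments, transfusions, growth factors etc. will be administered at the discretion of the investigators". Extra time for counts is tied to one category: "If the response is CRi without adequate blood count recovery between Day 21-28, the cycle will be prolonged up to two weeks" (three weeks in the second induction cycle).

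Under Protocol 10.4.2 and SAP 7.2.1, induction failure is an EFS event dated at randomization. SAP 7.2.1 defines it as no CR, or CRi with adequate recovery, up to 93 days after induction starts.

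**The concern.** There are two separate faults in the rule that decides the induction component of the primary endpoint.

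The first is a hole. Transfusion status bars a patient from CR, but the CRi rows accept only patients whose counts fall short of CR. A patient with full counts and a recent transfusion is therefore shut out of both. A patient with lower platelets and the same transfusion is admitted, so better recovery gives the worse category.

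The second is a contradiction. Whether CRi with adequate recovery needs two transfusion-free days depends on which section is read. Platelets of 55 on the day after a platelet transfusion are a response under Table 7-2 and not under 7.2.1.6.

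The same status determines the EFS events placed at time zero, the CR/CRi rate, and who enters the DFS, CIR and CID analyses (SAP 8.3). The SAP repeats the response labels and lists transfusions, but gives no rule for combining the two when deriving response.

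**Working it through.** **1. Classification.** Assume a clear marrow (blasts below 5%, no Auer rods), no blood blasts and no extramedullary disease. PR is then impossible, because it needs Auer rods or at least 5% blasts. The illustrative counts below run through each row of Table 7-2, first alone and then with the 7.2.1.6 convention applied to CRi with adequate recovery.

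| Neutrophils | Platelets | Transfused in last 2 days | Table 7-2 alone | Adding 7.2.1.6 |
|---|---|---|---|---|
| 1.2 | 120 | no | CR | CR |
| 1.2 | 120 | yes | **No Response** | **No Response** |
| 1.2 | 70 | no | CRi, adequate | CRi, adequate |
| 1.2 | 70 | yes | **CRi, adequate** | **CRi, not adequate** |
| 1.2 | 40 | either | CRi, not adequate | CRi, not adequate |
| 0.8 | 40, 70 or 120 | either | CRi, not adequate | CRi, not adequate |

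Row 2 is the hole and row 4 is the contradiction. Sections 4.2 and the summary allow a third reading of row 2: platelets of 120 satisfy their threshold of at least 50, so an investigator working from those sections could record adequate recovery. The PR row confines its condition to neutrophil and platelet transfusions. The CR row does not, so a red-cell transfusion also counts against CR.

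**2. Route to an EFS event.** The maximum induction length in Protocol 7.2.1 is 28 + 14 + 1 + 28 + 21 + 1 = 93 days. A patient in row 2 becomes an EFS event only if no qualifying assessment is recorded in that time. Scheduled reassessment does not help, because it covers only CRi without adequate recovery. SAP 6.7.1 likewise plans a 28-day cycle for No Response. Unscheduled assessment is available when clinically indicated.

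The next treatment step is also unclear. Sections 4.2.1 and 7.2.1 send patients without CR, or CRi with adequate recovery, to a second induction, whereas 6.1.1.1 ties that to at least 5% blasts.

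The hole affects induction failure, not relapse: Table 7-2 defines relapse by blasts or extramedullary disease, without reference to transfusion.

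**3. The plan's own design figure.** Inputs from Protocol 10.7, 10.8 and the summary: HR 0.675, one-sided 2.5%, 1:1 allocation, 285 events, 90% power. Freedman's formula gives 280 events and Schoenfeld's 273; a fixed design with 285 events has power 0.913. A group sequential simulation used looks at 114, 223 and 285 events, a futility bound at HR 0.97, p < 0.0001 at the second look and p < 0.025 at the end:

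| True HR | Quantity | Simulated | Table 10-2 |
|---|---|---|---|
| 0.675 | Power | 0.901 | 0.900 |
| 0.675 | Futility stop | 0.026 | 0.025 |
| 1.0 | Type I error | 0.0236 | 0.024 |
| 1.0 | Futility stop | 0.565 | 0.558 |

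The plan's figure is reproduced.

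**4. Sensitivity on an assumed share.** Let *s* be the share of the 285 events that are false induction failures, equal in both arms. The diluted hazard ratio is approximately 0.675^(1 − s). The documents give no value for *s*; 0–10% is an assumption.

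| s | False events (285 × s) | HR | Group sequential power |
|---|---|---|---|
| 0 | 0 | 0.675 | 0.901 |
| 1% | 2.9 | 0.678 | 0.895 |
| 2% | 5.7 | 0.680 | 0.889 |
| 3% | 8.6 | 0.683 | 0.883 |
| 5% | 14.3 | 0.688 | 0.870 |
| 10% | 28.5 | 0.702 | 0.833 |

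This covers only one direction. Counting transfusion-supported platelets of 50 to below 100 as response works the opposite way, by removing events from time zero.

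**The case against.** The strongest reply is that none of this shows a wrong EFS event. Response is judged over as many as two cycles and 93 days, and assessment at any time is allowed. In the second cycle, the Day 21–28 marrow can be used retrospectively to Day 49, so one blood count after two transfusion-free days would turn the row 2 patient into a CR. EFS rests on investigator judgment, and nothing shows that Table 7-2 is applied mechanically. Sections 4.2 and the summary, with no upper platelet limit, could lead an investigator to record this patient as a responder. The bracket in 7.2.1.6 naming only CR weakens the claim that it requires transfusion freedom for CRi.

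Most of this stands as to size. A reader might infer that primary EFS failures have been misclassified, that some percentage of patients is affected, or that unequal transfusion practice biases the comparison. The documents support none of these: no frequency is given, one transfused assessment is not a failure, and the trial was double-blind while it was running.

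The reply does not remove the defect. The missing platelet limit and the bracketed CR add readings; they do not settle which one governs. Response needs no confirmation by a repeat test (protocol summary), roughly 150–180 sites were planned (Protocol 4.1), and no step to harmonize readings is described.

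**Conclusion.** The concern holds as a defect in the endpoint definition. Followed literally, Table 7-2 ranks full counts with a recent transfusion below lower counts with the same transfusion. Table 7-2, 7.2.1.6, 4.2 and the summary cannot all be applied as written. Induction response, EFS events dated at randomization, the CR/CRi rate and the DFS, CIR and CID populations can therefore be misclassified or classified differently by different investigators, in either direction.

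The effect size is unknown. The sensitivity table assumes equal false failures in both arms and an arbitrary share; its power column is a design-stage illustration only. The trial stopped for futility at the first interim analysis, and the SAP provides no p-values for the final report. What remains at stake is the reported EFS estimate and the response-based summaries. The classification result rests on the wording alone and needs no assumed rate.

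**What to change.** Reconcile Table 7-2, 7.2.1.6, 4.2, the summary and the SAP for **endpoint derivation**:

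- State one transfusion rule, naming the blood products and the time window, and apply it identically to CR and to CRi with adequate recovery.
- Give full counts with a recent transfusion a defined category that is not No Response and does not rank below lower counts.
- State the same platelet limits wherever adequate recovery is defined.

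The current SAP was finalized after unblinding, so the choice of reading should not rest on one post hoc decision. Report EFS and the CR/CRi rate under each reading of the current text as a sensitivity analysis, using the transfusion dates already collected.

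In SAP 8.3.7, the 48-hour condition is written only against platelets of at least 50. State whether it also covers platelets of at least 100, as the lead-in on transfusion-independent platelet recovery implies, and the composite recovery definition.

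The passages that use response status to prolong cycles, give a second induction or move patients between phases (Protocol 4.2.1, 6.1.1.1 and 7.2.1) must be reconciled with each other. No clinical rule is proposed here.

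The cost is modest wording and programming, with no new visits or data. A few responses may be reclassified or dated later.
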